1. AMENDMENT HISTORY

| Protocol version no. | Effective Date | Significant Changes | Previous protocol version no. |
|----------------------|----------------|--|-------------------------------|
| 1.1 | 25.07.2016 | Primary outcome measure re-defined. Revision of chapter 13. Clarification on the patient identifier. (changes made as requested by the Ethics Committee) | 1.0 |
| 1.2 | 14.09.2016 | 2 Investigators added | 1.1 |
| | | | |
| | | | |

3. SYNOPSIS

| | |
|---------------------|--|
| Study Title | Multimodal Assessment to Optimise the Result of Percutaneous Coronary Interventions. The OXOPT-PCI study |
| Study Design | Prospective single centre clinical trial |

| | | | |
|-------------------------|-------------------|--------------------------|--------------------|
| Subject: | Research Protocol | Ethics Ref/ IRAS number: | 16/SC/0394/ 204681 |
| Principal Investigator: | [name] | Version/Date: | V1.2_14.09.2016 |
| Short Title: | OXOPT-PCI study | Page: | 4 of 31 |

| | |
|-------------------------------|---|
| Study Participants | Pts aged 30-90 presenting for coronary angiography and PCI |
| Number of Participants | 100 |
| Treatment duration | Maximum of 30 minutes |
| Follow up duration | 12 months |
| Planned Study Period | 1 year |
| Primary Objective | To assess the impact of a study specific treatment algorithm on final FFR after PCI measured in the target vessel. |
| Secondary Objectives | The OXOPT-PCI study aims to assess the frequency of intracoronary pathologies after PCI that potentially lead to an impaired FFR using OCT according to CLI-OPCI II study criteria. |
| Tertiary Objectives | 
 1. To assess the impact of a study specific treatment algorithm on final parameters of coronary physiology after PCI measured in the target vessel. 2. To assess the impact on clinical outcome. |
| Intervention (s) | Optimisation of PCI result according to a study specific algorithm |

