6. OBJECTIVES AND OUTCOME MEASURES/ENDPOINTS

| Objectives | Outcome Measures/Endpoints |
|---|--|
| Primary Objective To assess the impact of a dedicated treatment algorithm on final FFR after PCI measured in the target vessel. | Proportion of patients with FFR >0.9 at baseline versus proportion of patient with FFR measured at the end of optimisation procedure (final FFR) |
| Secondary Objectives The OXOPT-PCI study aims to assess the frequency of intracoronary pathologies after PCI that potentially lead to an impaired FFR using OCT according to CLI-OPCI II study criteria. | 1. Frequency of: 
 - Stent-edge dissection - Geographical miss/Reference lumen narrowing - Stent-malapposition - In-stent minimum lumen area (MLA) < 4.5 mm² - In-stent MLA <70% of the average reference lumen area - Intrastent plaque/thrombus protrusion 2. Frequency of a significant pressure step up during pressure wire pullback during maximal hyperaemia. |
| Tertiary Objectives 
 1. To assess the impact of a dedicated treatment algorithm on final parameters of coronary physiology after PCI measured in the target vessel. 2. To assess the impact on clinical outcome. | 1. Coronary flow reserve (CFR), index of microcirculatory resistance (IMR) measured at the end of PCI. 2. Composite of death, myocardial infarction and target vessel revascularisation after 12 months of follow up. |

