
assessment and discharge strategy will be carried out according to routine clinical practice. Telephone follow-ups will be then performed at 12 months to assess current symptoms and cardiovascular events. The end of the study for each patient will be the date of the 12 months telephone follow-up.

This is a clinical trial in attempt to give some insights regarding the utility of a specific multi-modal algorithm to improve the result of PCI. In view of the absence of data on this topic, it has been designed as pilot study for power analysis and sample size calculation of a further main study.¹¹ Based on this assumption it was designed as a non-randomised clinical trial.

Comments from an external peer review have been considered when finalising this protocol.

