10. STUDY PROCEDURES

10.1 Study timeline (see “Integrated flowchart for OXOPT-PCI study” as in Appendix 1)

10.2 Recruitment

Participants will be identified by the clinical care team from pre-angiogram clinic or angiogram procedure waiting lists. They will be posted or given an invitation letter and information leaflet with reply slip, either with their appointment letter or whilst awaiting the PCI procedure as an inpatient. If patients are willing to participate, they may return the reply slip and/or inform the clinical care team at their consultation who will then inform study investigators. Inpatients will have a minimum of 24 hours to consider their participation in this study.

Based on the annual audit data ~1500 PCI are performed at the JR Hospital (~30 per week). Of these 30 cases at least > 50% would fulfil the inclusion criteria of the present study. These numbers justify the feasibility of the suggested 100 participants over the time of 1 year.

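### Does a planned study period of 1 year leave no room for the 12-month follow-up?

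*Protocol*

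**What the plan says.** The synopsis (Protocol, section 3) carries three relevant rows: "Number of Participants | 100", "Follow up duration | 12 months" and "Planned Study Period | 1 year". It does not say whether the last means the enrolment window or the whole span from first enrolment to last contact.

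Section 10.2 supports recruitment with the centre's workload: "Based on the annual audit data ~1500 PCI are performed at the JR Hospital (~30 per week"), and "Of these 30 cases at least > 50% would fulfil the inclusion criteria of the present study". It concludes: "These numbers justify the feasibility of the suggested 100 participants over the time of 1 year".

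Section 7 fixes when a patient leaves the study: "The end of the study for each patient will be the date of the 12 months telephone follow-up". Section 6 lists the outcome that depends on that call, as a tertiary endpoint: "Composite of death, myocardial infarction and target vessel revascularisation after 12 months of follow up".

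**The concern.** A year of enrolment followed by a year of follow-up for the last patient takes two years, yet the synopsis states one. Taken literally as total duration, the row would have the study close when recruitment closes. Only a patient treated on the first day could then reach the 12-month call.

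With steady accrual and closure at month 12, follow-up would average 6 months and the clinical composite would be cut short for nearly everyone. That would matter beyond this study, because section 7 describes it as a pilot meant to inform the sample size of a larger one. An event rate from truncated follow-up would be a poor input if that larger study used a clinical endpoint.

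**Working it through.** **Inputs.** All come from the Protocol except uptake.
- 100 patients (section 3).
- About 30 PCI per week, of which at least half are eligible (section 10.2). Taking half, 30 × 0.5 = 15 eligible per week, or 15 × 52 = 780 per year.
- Recruitment window of 1 year (section 10.2).
- 12 months of follow-up per patient (sections 3, 6 and 7).
- The share of eligible patients who consent is not given in the text that could be read, so it is varied below as an assumption.

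**Can the stated 1 year be reproduced?** Yes, if it means recruitment. Enrolling 100 patients in 52 weeks needs 100/52 = 1.9 per week, or 100/780 = 12.8% of those eligible. That matches the window in section 10.2.

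**Can it be reproduced as total duration?** No. Total months = recruitment weeks × 12/52 + 12, where recruitment weeks = 100/(15 × uptake).

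| Uptake among eligible | Recruitment (weeks) | Recruitment (months) | First patient in to last call (months) |
|---|---|---|---|
| 100% | 6.7 | 1.5 | 13.5 |
| 75% (assumed) | 8.9 | 2.1 | 14.1 |
| 50% (assumed) | 13.3 | 3.1 | 15.1 |
| 25% (assumed) | 26.7 | 6.2 | 18.2 |
| 12.8% (full year used) | 52.0 | 12.0 | 24.0 |

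No row reaches 12 months. A higher eligible share would shorten recruitment but could not bring it to zero. The 24-month figure belongs to the full window; section 10.2 offers that year as feasible, not as a minimum.

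**What would truncation cost, if it happened?** Assume uniform accrual over 12 months, closure at month 12 and a constant hazard λ per year. The observed risk is then 1 − (1 − e^(−λ))/λ. As illustrations, take the two one-year MACE rates that section 5.1 reports from a cited drug-eluting stent study:
- 12.5%: λ = −ln(0.875) = 0.1335; observed risk = 1 − 0.125/0.1335 = 6.4%.
- 2.5%: λ = −ln(0.975) = 0.02532; observed risk = 1 − 0.025/0.02532 = 1.3%.

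About half the events would be missed. These rates are not projections for this trial, and the whole calculation depends on closure at month 12.

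**Does the Protocol plan that closure?** Section 7 places the end of study at each patient's own 12-month call, and section 6 defines the composite over 12 months. The contents page also lists a 12-month telephone follow-up as section 10.7. Nothing in the text that could be read stops follow-up on a calendar date.

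**The case for a change.** The best case for a correction is that study duration is a protocol-level statement, not something left to an analysis plan. Follow-up has its own row next to the study period, so a reader may well take the latter as the total. On that reading the figure is wrong at every recruitment speed, and putting it right would cost one label or one number. All of this is accurate, and the row is unclear.

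What does not stand is the harm. For data to be lost, staff would have to let an undefined synopsis entry override the follow-up rule in section 7 and the endpoint definition in section 6. A team applying those sections would carry on calling patients until the last one reached 12 months.

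One limit on this check: section 10.9 (Definition of End of Study) appears in the contents, but its text was not available here. It could settle what the row means.

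**Conclusion.** The arithmetic behind the concern is right on one reading: as a total duration, 1 year falls short by about 1.5 to 12 months, depending on how fast patients are enrolled. As a recruitment period, the same figure agrees with every section cited. The operative text fixes follow-up patient by patient, so under either reading the 12-month composite is collected as planned, and the estimated loss of half the events describes a closure that the readable text does not provide for.

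The primary FFR comparison, the OCT findings and the CFR and IMR measurements are all made at the procedure and do not depend on study length. Nor does any power calculation, threshold or analysis in the text that could be read draw on the row. The slip is clerical. Tidying the label would be reasonable housekeeping at the next revision, but it would alter neither what is measured nor what is concluded.

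This rests on two assumptions: that staff follow section 7 for each patient, and that section 10.9 does not impose an earlier calendar end.

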4. ABBREVIATIONS

| | |
|------|--|
| BMS | Bare metal stent |
| CFR | Coronary flow reserve |
| CI | Chief Investigator |
| DES | Drug eluting stent |
| FFR | Fractional flow reserve |
| GCP | Good Clinical Practice |
| IC | Informed Consent |
| ICF | Informed Consent Form |
| IMR | Index of microcirculatory resistance |
| MACE | Major adverse cardiac events |
| OCT | Optical coherence tomography |
| PCI | Percutaneous coronary intervention |
| PI | Principal Investigator |
| PIL | Participant/ Patient Information Leaflet |
| POBA | Plain old balloon angioplasty |
| R&D | NHS Trust R&D Department |
| REC | Research Ethics Committee |
| SOP | Standard Operating Procedure |

5. BACKGROUND AND RATIONALE

Fractional flow reserve (FFR) is the established gold standard used in the cardiac catheterisation laboratory to assess the haemodynamic relevance of coronary artery stenoses before stenting. Evidence from various clinical scenarios has shown that an FFR-guided PCI strategy reduces the need for stenting and improves clinical outcomes. Therefore, FFR has been incorporated in current revascularisation guidelines.¹⁻³

Visual assessment of the interventional result by angiography and quantitative coronary angiography (QCA), has limited efficacy with respect to identifying patients with suboptimal PCI results and subsequent worse clinical outcomes.^{4, 5} Post-PCI FFR measurement has been shown to be a useful indicator for the identification of a suboptimal PCI result in small observational studies using older techniques including plain old balloon angioplasty (POBA), bare metal stents (BMS) and first/ second generation drug eluting stents (DES).

5.1 Post-PCI FFR as an indicator of clinical outcome

In 1999, Bech et al. demonstrated that FFR was useful for stratifying patient outcome after plain old balloon angioplasty (POBA).⁷ Receiver operating characteristics (ROC) curve analysis identified a post-POBA FFR of 0.89 as optimal predictor for worse clinical outcome at two years follow up (MACE rate: 40.6 vs. 11.5%; area under curve (AUC) = 0.69).

This was subsequently confirmed for PCI using bare metal stents. Pijls et al. showed that FFR after BMS implantation was an independent predictor of clinical outcome at 6 months.⁶ In this study patients with a post-stent FFR <0.9 had a significantly worse outcome after 6 months than those with an FFR ≥0.9 (MACE rate: 20.3 vs. 5.5%). Analysing data for state of the art technologies showed that the FFR following implantation of drug-eluting stents (DES) predicted MACE at one year in a study reported in 2011.⁷ Receiver operating characteristics (ROC) curve analysis identified an FFR <0.90 as optimal predictor for worse outcome at one-year follow up (MACE rate: 12.5 vs. 2.5%, ROC analysis: sensitivity = 67%, specificity = 58%, AUC = 0.69, 95% CI = 0.53–0.86).

5.2 Causes of persistently low FFR after PCI

Retrospective studies using intra-coronary imaging have identified possible underlying causes for a suboptimal FFR, including incomplete stent expansion, stent malapposition, “geographical miss”, plaque protrusion, edge dissection, and plaque shift at the stent edge.

| | | | |
|-------------------------|-------------------|--------------------------|--------------------|
| Subject: | Research Protocol | Ethics Ref/ IRAS number: | 16/SC/0394/ 204681 |
| Principal Investigator: | [name] | Version/Date: | V1.2_14.09.2016 |
| Short Title: | OXOPT-PCI study | Page: | 7 of 31 |

(Figure 1).

[figure not shown]

Figure 1. Potential causes of suboptimal FFR after percutaneous coronary interventions. Panel A: 'geographical miss' (diseased reference segment). Panel B: stent mal-apposition. Panel C: stent under-expansion. Panel D: intrastent plaque-protrusion/thrombus. Panel E: edge dissection. MLA - minimal lumen area, REF - proximal reference segment.

5.3 Assessment of coronary physiology (coronary pressure/flow)

Coronary flow and pressure measurements are widely recognised to determine the degree of disease for epicardial vessels and for the microcirculation.⁸ The pressure wire is interchangeable with the coronary guide wire used in all PCI procedures, so is incorporated in to the procedure. Measurements that assess the integrity of the small blood vessels of the heart are made at the end of the PCI in response to administration of clinically used drugs such as adenosine to increase coronary flow. Saline is flushed through the guide catheter to measure coronary flow using the transit time calculation. Incorporating these parameters are recognised to support the clinical decision making but no standardized guidelines for their application after stenting has been established.

5.4 Imaging Modalities Used to Evaluate Coronary Artery Disease

5.4.1 Optical coherence tomography (OCT)

| | | | |
|-------------------------|-------------------|--------------------------|--------------------|
| Subject: | Research Protocol | Ethics Ref/ IRAS number: | 16/SC/0394/ 204681 |
| Principal Investigator: | [name] | Version/Date: | V1.2_14.09.2016 |
| Short Title: | OXOPT-PCI study | Page: | 8 of 31 |

OCT is a high resolution intravascular imaging modality that can accurately characterise coronary morphology.⁹ Recently a study evaluating the relationship between final stent dimensions, determined by optical coherence tomography (OCT), post-stent FFR, and clinical outcome the intrastent area stenosis (AS) was positively correlated with post-stent FFR ($r^2 = 0.49$; $P < 0.001$), and both parameters were good predictors of MACE rate at 20-month follow up.¹⁰ The optimal thresholds to predict MACE was 0.905 for post-stent FFR, based on ROC analysis (sensitivity 71.4%, specificity 85.0%, AUC 0.77, 95% CI 0.56–0.97).

5.5 Background Summary

Based on available evidence a persistently low FFR following PCI is associated with an adverse clinical outcome. Small observational studies using intra-coronary imaging have suggested different underlying causes for a suboptimal FFR. The aim of this prospective clinical trial is to confirm that these are the responsible mechanisms and to examine whether additional simple procedures can influence post-stent FFR and potentially improve clinical outcome.

5.6 Study Hypothesis

1) A post PCI FFR < 0.9 is linked to a suboptimal stent deployment. 2) Using a dedicated algorithm incorporation FFR measurements and intracoronary imaging will improve interventional result.

6. OBJECTIVES AND OUTCOME MEASURES/ENDPOINTS

| Objectives | Outcome Measures/Endpoints |
|---|--|
| Primary Objective To assess the impact of a dedicated treatment algorithm on final FFR after PCI measured in the target vessel. | Proportion of patients with FFR >0.9 at baseline versus proportion of patient with FFR measured at the end of optimisation procedure (final FFR) |
| Secondary Objectives The OXOPT-PCI study aims to assess the frequency of intracoronary pathologies after PCI that potentially lead to an impaired FFR using OCT according to CLI-OPCI II study criteria. | 1. Frequency of: 
 - Stent-edge dissection - Geographical miss/Reference lumen narrowing - Stent-malapposition - In-stent minimum lumen area (MLA) < 4.5 mm² - In-stent MLA <70% of the average reference lumen area - Intrastent plaque/thrombus protrusion 2. Frequency of a significant pressure step up during pressure wire pullback during maximal hyperaemia. |
| Tertiary Objectives 
 1. To assess the impact of a dedicated treatment algorithm on final parameters of coronary physiology after PCI measured in the target vessel. 2. To assess the impact on clinical outcome. | 1. Coronary flow reserve (CFR), index of microcirculatory resistance (IMR) measured at the end of PCI. 2. Composite of death, myocardial infarction and target vessel revascularisation after 12 months of follow up. |

7. TRIAL DESIGN

The OXOPT-PCI study is a prospective single centre clinical trial investigating the use of a dedicated, study specific treatment algorithm on the final result of PCI in patients with suspected or known coronary artery disease, including acute myocardial infarction (except for ST elevation myocardial infarction), who present for coronary angiography with the usual expectation of proceeding to PCI.

Patients, age 30-90, will be included in the study. Informed consent will be obtained prior to the angiography/ PCI procedure.

A flowchart of the study design, indicating the time points and procedures, is shown in Appendix A.

All PCI procedures, coronary imaging and coronary physiology measurements will be performed in a standard fashion. A specific treatment algorithm incorporating parameters of coronary imaging and coronary physiology will dictate further optimisation of the stent result (Figure 2, Chapter 10.5.). After stenting all patients will undergo intravascular imaging with OCT and in all patients the FFR will be assessed in the stented vessel. The initial stent result will be optimised based on intravascular imaging if clinically indicated by the CLI-OPCI II study criteria (see chapter 10.5.3). Following optimisation of the stent result the OCT assessment and the FFR measurement in the target vessel will be repeated. At this stage the study population will be divided into two groups according to the latter FFR recording.

Group A includes patients with an FFR value <0.9. In these patients the OCT images will be used to decide according to the CLI-OPCI II criteria whether and how to optimise the stent result (see chapter 10.5.5). If further optimisation was carried out the intervention will be concluded by repeated assessment of coronary physiology (FFR, CFR, IMR) and intravascular imaging. If no further stent-optimisation was performed the intervention will be concluded by the assessment of CFR and IMR.

Group B includes all patients with an FFR ≥ 0.9 . As this FFR value can be considered satisfactory, no further optimisation of the interventional result will be attempted and the PCI will be concluded by the assessment of CFR and IMR. Procedural details including details of the PCI, the coronary physiology measurements and intravascular imaging studies (OCT-studies) at all stages of the study and of all study patients will be recorded. The total procedure and PCI/ OCT/ coronary physiology study times will be also collected. Post-PCI

assessment and discharge strategy will be carried out according to routine clinical practice. Telephone follow-ups will be then performed at 12 months to assess current symptoms and cardiovascular events. The end of the study for each patient will be the date of the 12 months telephone follow-up.

This is a clinical trial in attempt to give some insights regarding the utility of a specific multi-modal algorithm to improve the result of PCI. In view of the absence of data on this topic, it has been designed as pilot study for power analysis and sample size calculation of a further main study.¹¹ Based on this assumption it was designed as a non-randomised clinical trial.

Comments from an external peer review have been considered when finalising this protocol.

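### As Section 7 is written, FFR after the 0.9 split is repeated only in re-optimised Group A patients; if the split reading counts as final FFR in the others, the primary proportion is biased upward in expectation, probably by a small amount

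*Protocol*

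**What the plan says.** The primary outcome (Protocol, Section 6) is: "Proportion of patients with FFR >0.9 at baseline versus proportion of patient with FFR measured at the end of optimisation procedure (final FFR". The text available does not define baseline, and it does not say which reading is the final FFR in a patient with no later one.

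Section 7 gives the order of measurements:

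- After stenting: "After stenting all patients will undergo intravascular imaging with OCT and in all patients the FFR will be assessed in the stented vessel".
- After the first, OCT-triggered step: "Following optimisation of the stent result the OCT assessment and the FFR measurement in the target vessel will be repeated". This reading splits the patients into Group A (below 0.9) and Group B (0.9 or above).
- Group A, optimised again: "If further optimisation was carried out the intervention will be concluded by repeated assessment of coronary physiology (FFR, CFR, IMR) and intravascular imaging".
- Group A, not optimised again: "If no further stent-optimisation was performed the intervention will be concluded by the assessment of CFR and IMR".
- Group B: "no further optimisation of the interventional result will be attempted and the PCI will be concluded by the assessment of CFR and IMR".

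Section 8.1.1 likewise names only IMR and CFR as the final assessment. Section 6 lists as a tertiary outcome: "Coronary flow reserve (CFR), index of microcirculatory resistance (IMR) measured at the end of PCI". Section 5.3 describes the end-of-procedure measurements as made under a drug such as adenosine, so a closing pressure-wire run is planned in every patient. Section 7 also says that the study is a non-randomised pilot meant to inform the sample size of a later study.

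**The concern.** The rule that decides who is measured again uses the cut-off that defines success. A patient whose true FFR is above 0.9 but who reads below it by error may be re-optimised, read again and reclassified as a success. A patient whose true FFR is below 0.9 but who reads above it by error is never read again and stays a success. After the split, error can move a recorded value across 0.9 in one direction only.

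Part of the before-after gain can therefore be a re-measurement artefact. There is no control group to absorb it, and the gain is an output that the pilot passes on to later planning.

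**Working it through.** **Inputs.** The Protocol gives the measurement schedule, the 0.9 cut-off and n = 100. It gives no measurement error, no FFR distribution for this population and no re-optimised share, so these are assumed: true FFR N(0.88, 0.065); single-reading error SD e = 0.01, 0.02 or 0.03; share r of Group A re-optimised = 10, 25 or 50%, unrelated to FFR within Group A. In this model 61 to 62% of patients fall in Group A. The plan states no figure to reproduce.

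**Step 1, direction.** Let R1 be the split reading and R2 a repeat, with the same error distribution. Define c = P(R1 < 0.9 and R2 > 0.9). Compare carrying R1 forward with taking a closing FFR in everyone:

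- Group B patients whose repeat would not exceed 0.9 stay successes: + c.
- Group A patients not re-optimised whose repeat would exceed 0.9 stay failures: − (1 − r)c.
- Re-optimised patients are read again either way: 0.

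Net bias = c − (1 − r)c = r × c. No treatment-effect term appears. If re-optimised patients are selected in some other way, the bias is the proportion of all patients who are re-optimised and would have read above 0.9 on a repeat with no effect, which also cannot be negative.

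The first optimisation step adds no such bias, because Section 7 makes OCT criteria, not FFR, its trigger.

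**Step 2, size.** R1 and R2 are bivariate normal with variance 0.065² + e² and covariance 0.065². Then c = P(R1 < 0.9) − P(R1 < 0.9, R2 < 0.9). Bias in percentage points:

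| Error SD | c | r = 10% | r = 25% | r = 50% |
|---|---|---|---|---|
| 0.01 | 3.27% | 0.33 | 0.82 | 1.64 |
| 0.02 | 6.38% | 0.64 | 1.60 | 3.19 |
| 0.03 | 9.20% | 0.92 | 2.30 | 4.60 |

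**Step 3, two-decimal recording.** Group A is then 0.89 or below and success is 0.91 or above, so c = P(R1 < 0.895 and R2 > 0.905) = 1.16 / 3.96 / 6.76%. The bias is 0.12 / 0.40 / 0.68 points at r = 10% and 0.29 / 0.99 / 1.69 at r = 25%.

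**Step 4, other assumptions (unrounded).**

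- Half the error variance shared between readings: c = 2.31 / 4.50 / 6.46%, so 0.58 / 1.12 / 1.61 points at r = 25%.
- Re-optimised patients mainly those with clearly low true FFR (simulated): 0.1 to 0.3 points at 12% re-optimised, 0.2 to 0.9 at 30%.
- FFR mean 0.86 to 0.92 and SD 0.05 to 0.08: 0.25 to 1.19 points at r = 10%, 0.62 to 2.96 at r = 25%.
- 30 to 45% of patients below 0.9, a range suggested by the drug-eluting-stent cohort cited in Section 5.1: 0.7 to 3.0 points at r = 25%.

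**Step 5, simulation with no true effect (n = 100, r = 25%).** The mean gain with carry-forward is 0.80 / 1.58 / 2.31 points; with a closing FFR in everyone it is 0.0. No value moves downward across 0.9 after the split.

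**The case against.** **The definition may stand elsewhere.** Section 7 is a summary. Chapters 10.5.3 to 10.5.5, 11.2 and 13, Figure 2 and Appendix A are not available here, and the contents list has a stage headed as the end of the procedure. Section 7 also says that physiology data from all stages and all patients will be kept. That sentence covers what is measured and does not schedule another FFR. The objection stands as a condition on the finding.

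**The sign needs equal error distributions.** This is correct. With error SD 0.02, an upward drift of 0.01 between split and closing readings makes the carried-forward proportion differ from a closing FFR in everyone by −4.7 / −3.3 / −0.8 points at r = 10 / 25 / 50%. A reader might infer that the bias can never be negative; that holds only without drift.

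**It is small beside sampling error.** Also fair. If every patient were re-read once with error SD 0.02 and no effect, the standard error of the change would be √(2 × 0.0638 / 100) = 3.6 points. At r = 10% the bias is below one patient in 100. Because the second step uses the OCT criteria already applied at the first, high re-optimised shares may be unlikely. But sampling error averages out over repeated studies and this bias does not.

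**An analysis plan could settle it.** A reader might infer that the missing readings are lost for good. The documents do not support that: if the closing run stores the pressure ratio, a definition is enough.

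**Conclusion.** The point holds, conditionally, and is worth fixing. As Section 7 is written, re-measurement after the split is selected on the endpoint's own threshold, and the primary proportion is biased upward in expectation. This rests on two assumptions: the split reading serves as final FFR in patients with no later one listed, and split and closing readings share an error distribution.

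Reading the whole gain as an optimisation effect further requires baseline to mean post-stent FFR. Section 5.5 supports that by stating the aim "to examine whether additional simple procedures can influence post-stent FFR and potentially improve clinical outcome". If baseline meant pre-stent FFR, the artefact would still sit in the final proportion but would be a smaller part of the gain.

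The size is unknown and probably small: about 0.3 to 2.3 points under the main assumptions at 10 to 25% re-optimised, or about 0.1 to 1.7 with two-decimal recording. It is materially larger only if many patients are re-optimised.

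Three stronger readings are not supported. The available text names no test, so no false-positive rate can be claimed. It gives no design or effect size for the later study, so no shortfall in that study's size can be calculated. And the bias is an expectation: in the no-effect simulation the proportion still fell in 19 to 25% of single trials.

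**What to change.** State both readings in the primary outcome, for example: *Baseline FFR is the post-stent FFR before any optimisation. Final FFR is the FFR recorded at the closing hyperaemic pressure-wire assessment in every patient: Group A with or without further optimisation, and Group B.* Take it from the run already planned for CFR and IMR. This removes the selection; it does not remove drift, which an uncontrolled design cannot separate from effect.

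Three checks need no readings beyond those in Section 7:

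- Post-stent FFR against FFR at the split. Neither is selected on FFR, but this covers the first step only.
- The paired mean change in FFR with a 95% CI. With no effect, its bias is at most 0.0025 FFR units at shares up to 50%.
- The number of Group A patients re-optimised, with their split and final FFR. In the absence of drift, that number caps the bias.

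The cost is one more recorded value per patient, or at most one more reading within the same closing assessment if the run does not store the pressure ratio. The stated effect will probably look slightly smaller. If chapters 10.5, 11.2 or 13, Figure 2 or Appendix A already require a final FFR in everyone, it is enough to reconcile Section 7 with them.
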